The proposed study is a phase 2, open-label study of tofakinib in treatment of patients with chronic pouchitis. Patients with chronic active pouchitis will be recruited from the Cedars-Sinai Inflammatory Bowel Disease Center. The total expected duration of participation is 16 weeks including a 4-week screening period, 8 weeks of tofakinib therapy and an end of study visit 4 weeks after completion of 8-week tofakinib treatment. Subjects experiencing early withdrawal from study will be scheduled for a safety follow-up visit 4 weeks after the date of withdrawal. The primary outcome is a reduction in the mPDAI score ≥ 2 at week 8 compared to baseline. We will also assess secondary outcomes including changes in clinical symptoms, fecal calprotectin, HRQOL, and mucosal appearance.

Figure 1: Study Design

Study Population

The study will be open to adult patients (ages 18-80 years) seen at the Cedars-Sinai Inflammatory Bowel Disease Center who meet eligibility criteria.

Inclusion criteria

1. Male or female subjects ages 18 to 80

2. Subjects with a history of proctocolectomy with ileal pouch anal anastomosis (IPAA) for UC at least 6 months prior to screening.
3. Subjects with pouchitis that is chronic, defined by a mPDAI score ≥ 5 assessed as the average from 3 days immediately prior to the baseline study visit and a minimum endoscopic subscore of 2 (outside the staple or suture line) with either (a) ≥ 3 recurrent episodes within 1 year prior to the screening treated with ≥ 2 weeks of antibiotic or other prescription therapy, (b) requiring maintenance antibiotic therapy taken continuously for ≥ 4 weeks immediately prior to the baseline study visit, or (c) not responding to $>= 4$ weeks of antibiotic therapy.
4. Women of childbearing potential must have documentation of a negative pregnancy test at screening and must agree to use two highly effective methods of birth control during the study and for at least 1 month after completion of study drug dosing.
5. Subjects willing and able to give informed consent.

Exclusion criteria

1. Subjects with IPAA surgery done for Crohn's disease (CD) or familial adenomatous polyposis (FAP) indications.
2. Subjects with CD-like complications including non-anastomotic strictures and active perianal fistulae, isolated or predominant cuffitis or mechanical complications of the ileal pouch.
3. Surgical complications such as anal stenosis, anastomotic leak, or fistula.
4. Subjects with prior exposure to tofacitinib.

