18. Subjects with condition(s) that in the opinion of the study investigators, may interfere with the participants ability to comply with the study procedures.

Concomitant medications

Study subjects will be allowed to remain on permitted concomitant medications provided the patient is on a stable dose for \geq 2 weeks prior to starting tofacitinib. Patient will need to stay on stable doses of these medications for the study duration of 8 weeks.

1. Antibiotics
2. Antidiarrheal agents
3. Oral corticosteroids including budesonide, up to doses of prednisone 20mg daily (or equivalent), or budesonide 9mg daily.
4. Probiotics

The following medications will not be allowed during the study:

1. Azathioprine, 6-mercaptopurine, or methotrexate within the 28 days prior to dosing visit.
2. Adalimumab, infliximab, golimumab, etanercept, certolizumab or vedolizumab within the 60 days prior to the first study visit or with negative drug concentration
3. Ustekinumab within 120 days prior to the first dosing visit or with negative drug concentration.
4. Intravenous corticosteroids within the 14 days prior to the first dosing visit.
5. Topical mesalamine or topical steroid within the 14 days prior to the first dosing visit.
6. Mycophenolic acid, tacrolimus, or cyclosporine within 60 days prior to the first dosing visit.

Treatment with Tofacitinib

Eligible subjects will be given tofacitinib 10mg twice daily for an 8-week duration. Study drug will be supplied for 4 weeks each at the baseline and week 4 visits.

Study Visits and Procedures

There are 5 study visits and 2 pouch endoscopic procedures during this 12-week study.

Screening Period (Week -4 to Day 0)

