After giving informed consent, subjects will undergo up to a 4-week screening period to provide baseline data and be assessed for eligibility. The subjects will have a screening visit during which they will undergo an assessment of their medical history, symptom assessment and a complete physical examination with vital signs, height and weight measurement. They will also undergo complete blood count with automated differential, serum chemistries, serum C-reactive protein (CRP), lipid panel, QuantiFERON®-TB Gold test, urinalysis, fecal calprotectin, infectious stool studies, electrocardiogram (ECG), and chest X-ray. Subjects who satisfy the inclusion criteria and do not meet any exclusion criteria will proceed with pouch endoscopy with biopsies to confirm endoscopic eligibility and assess a baseline mPDAI endoscopic subscore. The pouch endoscopy will be scored by a central reader to reduce the risk of bias. If the subject meets all the eligibility criteria, he/she may be enrolled into the study. The subjects will be required to maintain a daily paper-based symptom diary starting immediately after the screening visit, although only symptoms during the 3 days preceding the study visits will be used for the calculation of the mPDAI score for the appropriate study visits.

Baseline Visit (Week 0)

At the baseline visit, subjects' eligibility for the study will be confirmed. Vital signs will be recorded, and a targeted physical examination will be performed. The symptom diary will be reviewed for calculation of the mPDAI score, and subjects will complete the CGQL questionnaire. At the end of the visit, the subjects will be given a 4-week supply of tofacitinib to be taken at a dose of 10 mg twice daily.

Week 4 and Week 8 Visit (± 3 days)

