At the week 4 and week 8 visit, the subjects will undergo assessment for concomitant medication use, adverse effects and compliance with the study drug. Physical assessment will include vital signs and a symptom driven targeted physical examination. Blood, urine and stool will be collected for hematology, chemistry, CRP, urinalysis and fecal calprotectin measurement. Symptom diary will be reviewed, and subjects will complete the CGQL questionnaire. At the end of week 4 visit, the second 4-week supply of the study drug will be dispensed to the subjects. At the end of 8 weeks, the subjects will stop taking the study drug and undergo a pouch endoscopy with biopsies for calculation of mPDAI score to assess treatment response. The pouch endoscopy will be scored by a central reader to reduce the risk of bias.

Week 12 (± 3 days) or Early Termination Visit

The week 12 visit will be the final visit. Subjects who are withdrawn earlier from the study (per study rules and subjects who withdraw consent) after receiving study medication will complete

an early termination visit. At this visit, subjects will undergo a physical assessment, review of medications, adverse event assessment and blood, urine and stool collection for hematology, chemistry, CRP, urinalysis and fecal calprotectin measurement. Symptom assessment and CGQL questionnaire completion will also be performed.

Table 1 - Schedule of Study Procedures and Visits

Study visit	Screening (Week -4 to day 0)	Baseline (Day 1)	Week 4	Week 8	Week 12
General					
Informed consent	x				
Medication/Medical History	x				
Smoking Status	x				
Height, weight, BMI	x	x	x	x	x
Vital Signs	x	x	x	x	x
12-lead ECG	x				
Physical Examination	x	x	x	x	x
Chest X-ray	x				
Tuberculosis and HBV testing	x				
Study Drug Dispensing		x	x		
Clinical, laboratory, endoscopic and safety assessments					
Pregnancy Test (females only)	x				
Urine pregnancy test		x	x		
Chemistry, Hematology, Urinalysis	x		x	x	x
Stool C. difficile test	x				
Fasting Lipid Panel	x		x	x	x
C-Reactive Protein	x		x	x	x
Pouch endoscopy and biopsies	x			x	
Fecal calprotectin	x		x	x	x
Symptom Assessments	x	x	x	x	x
Concomitant medications	x	x	x	x	x
mPDAI		x		x	
Adverse event assessment			x	x	x
CGQL		x	x	x	x

Evaluation and Outcomes

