The primary outcome of the study is clinical response at 8 weeks (defined below) as a measure of treatment efficacy. Other efficacy endpoints will include individual clinical, biochemical, and endoscopic assessments. Key secondary outcomes include assessment for safety and health-related quality of life.

Primary Endpoint

1. Proportion of subjects with clinical response defined as reduction in mPDAI score ≥ 2 from baseline at 8 weeks.

Secondary Endpoints

1. The proportion of subjects with clinical response, defined as an mPDAI score of ≥ 5 at 8 weeks with ≥ 2 -point decrease from the baseline score at 8 weeks.
2. The proportion of subjects with clinical remission at 8 weeks, defined as mPDAI score of < 5 with a ≥ 2 -point decrease from the baseline mPDAI score.
3. Change in mPDAI score at 8 weeks compared to baseline.
4. Change in mPDAI clinical sub-score at week 4 and week 8 compared to baseline.
5. Change in mPDAI endoscopic sub-score at week 8 compared to baseline.
6. Change in IBD-related quality of life as measured by Cleveland Global Quality of Life (CGQL) at week 4 and week 8 compared to baseline.
7. Safety, as determined by incidence of treatment-emergent adverse events. Adverse events of interest will include thromboembolic events and herpes zoster.

Efficacy Assessments

Efficacy measurement

The following will be used for definitions of clinical, biochemical, and endoscopic efficacy:

1. Clinical response defined as an mPDAI score of ≥ 5 at 8 weeks with a 2-point decrease from the baseline mPDAI score.
2. Clinical remission defined as mPDAI score < 5 after 8 weeks of treatment.
3. Change in mPDAI score from baseline to week 8.
4. Change in clinical and endoscopic mPDAI sub-scores from baseline to week 8.
5. Change in fecal calprotectin from baseline to week 8.
6. Change in serum C-reactive protein from baseline to week 8.

Symptom Diary

The subjects will be required to maintain a paper-based symptom diary to be completed daily starting after the initial screening visit. The symptoms recorded will include frequency of bowel movements, fecal urgency, abdominal pain/cramps, fever and blood in stools. The symptoms during the 3 days preceding the study visits will be used for the calculation of the mPDAI score for each study visits.

Pouch disease activity

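### One screening endoscopy read both admits subjects and serves as the only endoscopic baseline, and no masking to visit or order is stated; protection for half of the mPDAI is incomplete as written, though the dual use alone has a small effect

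*Combined protocol and SAP*

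**What the plan says.** Under Study Visits and Procedures: "There are 5 study visits and 2 pouch endoscopic procedures during this 12-week study". Table 1 places the endoscopies at screening and week 8, with none at the Day 1 baseline visit. The section Pouch disease activity says that the mPDAI is calculated at every visit, but with two endoscopies this creates no second endoscopic baseline.

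The screening endoscopy is done "to confirm endoscopic eligibility and assess a baseline mPDAI endoscopic subscore". Inclusion criterion 3 requires an endoscopic subscore of at least 2 and an mPDAI of at least 5, so this one read is an entry criterion in itself and supplies half of the other. At week 8 subjects "undergo a pouch endoscopy with biopsies for calculation of mPDAI score to assess treatment response". For both endoscopies the protection given is the same sentence: "The pouch endoscopy will be scored by a central reader to reduce the risk of bias".

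The primary endpoint is "clinical response defined as reduction in mPDAI score ≥ 2 from baseline at 8 weeks". Under Data Analysis, response and remission are descriptive, missing data count as non-response, and the mPDAI change is tested with the Wilcoxon signed-rank test at two-sided p < 0.05. About 12 subjects are expected, with no sample size calculation.

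**The concern.** Two mechanisms could produce apparent improvement without a drug effect.

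- **Selection on the baseline read.** Reads that happen to err upward are more likely to pass the entry gate. The same reads then serve as baseline, so the week 8 read tends to be lower by chance alone (regression to the mean).
- **Expectation at week 8.** A reader who knows that a recording is post-treatment may score it lower. Central reading takes scoring away from the local endoscopist, which is a real gain, but it does not hide the visit unless the plan says so. The entry read must come before enrolment, so as described it cannot be part of a random-order, visit-masked set.

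No control arm is described that would show how large either effect is. At stake are the response rate, the endoscopic subscore change, and the one significance test that uses the mPDAI.

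**Working it through.** The plan gives no reader error, power or bias figure, so there is nothing of its own to reproduce. The check is a simulation under no drug effect.

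**Inputs from the plan.** Subscores 0–6 each; entry if endoscopic ≥ 2 and total ≥ 5; response if the total falls by ≥ 2; n = 12; Wilcoxon test at two-sided 0.05, so 2.5% nominal in the direction of improvement.

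**Assumptions.** True endoscopic and clinical subscores independent, SD 1.2, equal means 2.5, 3.0, 3.5 or 4.0; reading error SD 0.5, 0.75 or 1.0. That makes 12 scenarios.

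**Model.** Observed subscore = true score + reading error, rounded and limited to 0–6. The fall in mPDAI is (B + C0) − (E8 + C8), where C0 and C8 are the clinical subscores, E8 is the week 8 endoscopic read, and B is one of three baselines: the entry read, a re-read by the same reader with error correlation 0.5, or a re-read with independent error.

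**Step 1: false response, clinical score held constant.**

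| Mean, reading SD | Entry read | Correlated re-read | Independent re-read |
|---|---|---|---|
| 2.5, 1.0 | 21.0% | 17.4% | 14.5% |
| 3.0, 0.75 | 10.3% | 9.3% | 8.3% |
| 4.0, 0.5 | 2.3% | 2.2% | 2.2% |

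- Effect of dual use = entry minus independent: at most 21.0 − 14.5 = 6.5 points, at least 2.3 − 2.2 = 0.1, median about 1.0 over the 12 scenarios.
- In subjects: 12 × 0.065 = 0.78 at most; 12 × 0.010 = 0.12 at the median. One subject is 1/12 = 8.3 points.
- Share that is plain reader noise, left by any baseline: from 14.5/21.0 = 69% to 2.2/2.3 = 96%.
- Realistic gain from a same-reader re-read: at most 21.0 − 17.4 = 3.6 points (0.4 of a subject), median about 0.5.

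**Step 2: Wilcoxon test, n = 12, false significant improvement.**

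- Clinical score constant: 0.7–10.6% with the entry read (above 2.5% in 6 of 12 scenarios), 0.6–3.9% with the correlated re-read, 0.6–1.4% with an independent one.
- Holding the diary constant flatters the re-read, because entry also selects on the diary through the total score. With visit-level fluctuation of SD 0.5 in diary and endoscopy, the entry read gives about 1.8–16% and the correlated re-read about 1.3–8%. Both ranges pass 2.5%: in most scenarios with the entry read, and in more than half with the re-read.
- False response with fluctuation SD 0.5–0.7: 12.3–33.2% with the entry read, 12.1–29.9% with the correlated re-read.

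**Step 3: expectation bias, illustration only.** A separate model used subscore means 3.5, SD 1.5, reliability 0.75, correlation 0.3 between subscores, and noise in the diary too. No-effect response is 18.3%. Lowering every week 8 endoscopic read by 0.5 point gives 28.2%, and by 1 point 40.1%. In subjects: 12 × (0.282 − 0.183) = 1.2 and 12 × (0.401 − 0.183) = 2.6. The shifts are invented to show sensitivity; nothing in the documents says that they occur.

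**The case against.** The strongest reply is that this is silence, not a contradiction. Central scoring is stated twice, reader procedures may sit in a separate document, and one sentence on masking might be enough. Dual use is worth about 0.12 of a subject at the median, and the response rate is descriptive with no benchmark. Non-responder imputation works in the opposite direction. The largest figures come from a mean subscore of 2.5, where only about 56–58% of modelled subjects pass the entry gates; with mean 3.5 or above and no fluctuation, one scenario of six puts the entry-read Wilcoxon rate above 2.5%. The re-read also delays endpoint scores.

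Much of this stands. It limits the weight of the point and rules out three stronger readings that a reader might infer:

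- That the reader is unmasked. The documents show only that masking is not stated.
- That regression from the screening read would explain much of an observed response. It is a small part even of the false response.
- That a masked re-read would restore the Wilcoxon error rate. It lowers the rate, and once the diary fluctuates it often stays above nominal.

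What does not stand is that one sentence on masking would do the same job. The entry read is made before enrolment, so only a later paired read can hide visit and order for both recordings.

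**Conclusion.** The point holds as an inexpensive improvement of low to moderate weight. The structure is plain in the documents: two endoscopies, one read used for both entry and baseline, and central reading without stated masking to visit or order. Protection for 6 of the 12 mPDAI points is therefore incomplete as written, not absent.

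The effect of dual use alone stays below one subject in 12 in every scenario tried. The effect on the Wilcoxon test can matter, but a re-read removes only part of it. Both results rest on assumed score distributions, reader error and error correlation. The case for acting rests mainly on closing the route for expectation bias at week 8, and for that the documents support no estimate, neither that it is large nor that it is likely.

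**What to change.** Keep the screening read for eligibility. Add to the Screening Period and Week 4 and Week 8 Visit sections, for example: *Recordings of both endoscopies are retained. After the last week 8 endoscopy, the central reader scores all screening and week 8 recordings in random order, with subject, date and visit removed.*

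- Use these paired reads (12 × 2 = 24) for the endoscopic subscore change, the mPDAI change and the 2-point response. Report the results with the eligibility read alongside.
- Exclude nobody because of the re-read, and report how many subjects re-read below the entry gate.
- State that regression to the mean in the diary score, biological fluctuation and the unblinded diary remain.
- If masking is already set in another document, cite it in these sections.

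**Cost.** About 24 re-reads by the existing reader, and retention of recordings, which the documents do not mention. Endpoint scores come only after the last subject, with enrolment planned over 28 months. Under the step 1 assumptions, 1.3–15.6% of enrolled subjects would re-read below the entry gate with error correlation 0.5 (12 × 0.156 = 1.9 subjects at most), or 1.8–22.4% with independent error. No procedure, visit or reader is added.

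**A separate inconsistency.** Secondary endpoint 2 gives remission as "defined as mPDAI score of < 5 with a ≥ 2 -point decrease from the baseline mPDAI score", while Efficacy measurement item 2 has "Clinical remission defined as mPDAI score < 5 after 8 weeks of treatment", with no required decrease. These must be reconciled whatever is decided on the re-read. The gap would matter more with it, because a subject whose re-read baseline is already below 5 could count as a remission without any change.

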5. Subjects with impending need for surgery.
6. Subjects with a diverting stoma.
7. Subjects with a prior history or risk factors for venous thromboembolism.
8. Subjects with active bacterial, parasitic, fungal, mycobacterial, or viral infection (including *C. difficile* and GI infections observed upon stool testing at screening), any infection requiring hospitalization or intravenous antibiotics within 3 months prior to screening, any infection requiring oral antimicrobial treatment within 2 weeks prior to screening.
9. Subjects with a history of latent or active tuberculosis or a positive QuantiFERON[®]-TB Gold result.
10. Subjects positive for hepatitis B virus (HBV) surface antigen, hepatitis B virus core antibody with a negative hepatitis B surface antibody or with detectable serum hepatitis B DNA.
11. Female subjects who are pregnant, lactating, breastfeeding or planning to become pregnant during the study or within 1 month after the last dose of study drug.
12. Female subjects of childbearing potential who are sexually active with non-sterilized male partners and do not agree to using two highly effective methods of contraception from signing of informed consent throughout the duration of the study and for 4 weeks after the last dose.
13. Subjects with clinically significant laboratory abnormalities at study screening including: AST or ALT $\geq 3x$ the upper limit of normal, alkaline phosphatase $\geq 2x$ the upper limit of normal,

total bilirubin \geq 2 mg/dL (unless confirmed diagnosis of Gilbert's), estimated creatinine clearance $<$ 60 mL/min, total white blood cell count (WBC) $<$ 3 \times 10⁹/L, absolute neutrophil count $<$ 1.3 \times 10⁹/L, absolute lymphocyte count $<$ 0.5 \times 10⁹/L, hemoglobin $<$ 8 g/dL, or platelet count $<$ 100 \times 10⁹/L.

14. Subjects with evidence of active or history of clinically significant endocrine, pulmonary, cardiovascular (including uncontrolled hyperlipidemia [defined as LDL $>$ 200 mg/dL, total cholesterol $>$ 300 mg/dL, triglyceride $>$ 500 mg/dL]), hepatic, GI, psychiatric, oncologic or neurological disease as determined by the investigator at screening.
15. Subjects with an active solid organ or hematological malignancy (except non-melanoma skin cancers), or a history of a solid organ or hematological malignancy within the last 5 years.
16. Subjects with an organ transplant.
17. Subjects who received a live vaccine within 4 weeks of screening visit.

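### No scheduled pregnancy test follows week 4, although dosing runs to week 8 and the plan's pregnancy-avoidance period runs to about week 12

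*Combined protocol and SAP*

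**What the plan says.** **Testing.** Inclusion criterion 4 says that women of childbearing potential "must have documentation of a negative pregnancy test at screening". Table 1 (Schedule of Study Procedures and Visits) has two rows. The one beginning "Pregnancy Test (females only" is marked at screening only. The one headed "Urine pregnancy test" is marked at baseline and week 4; its week 8 and week 12 cells are empty.

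**Dosing.** Under Treatment with Tofacitinib: "Eligible subjects will be given tofacitinib 10mg twice daily for an 8-week duration". The drug is handed out in two 4-week supplies, at baseline and at week 4. The description of the week 4 and week 8 visits adds: "At the end of 8 weeks, the subjects will stop taking the study drug".

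**Avoidance of pregnancy.** Three eligibility items carry the period past the last dose:
- Inclusion 4 requires contraception during the study and "for at least 1 month after completion of study drug dosing".
- Exclusion 11 bars women who are "planning to become pregnant during the study or within 1 month after the last dose of study drug".
- Exclusion 12 requires contraception "throughout the duration of the study and for 4 weeks after the last dose".

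**Other monitoring.** Table 1 schedules adverse event assessment and urinalysis at weeks 4, 8 and 12. The Safety Assessment section names the adverse events to be looked for; pregnancy is not among them.

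**The concern.** The plan treats pregnancy as something to be avoided throughout dosing and for about four weeks afterwards, but its last scheduled test comes when the second supply of drug is dispensed. A site that follows Table 1 exactly would complete a woman's participation at week 12 with her last test some eight weeks earlier. A woman who stopped before week 4 would have been tested last at baseline, because the early termination visit description lists no pregnancy test.

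Two things are at stake. The first is participant safety: a woman could take some or all of the second supply while unknowingly pregnant, or leave the study without knowing. The second is reporting. Safety is Objective 2, and a count of exposed pregnancies would rest on scheduled testing for the first four weeks and on spontaneous recognition after that.

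**Working it through.** No statistical figure is involved; the check is calendar arithmetic, with the first dose as day 0.

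**Inputs**
- Last scheduled test: week 4, with a window of ± 3 days (Table 1; week 4 and week 8 visit heading).
- End of dosing: week 8, same window if tied to the visit.
- End of avoidance period: 4 weeks or 1 month after the last dose (inclusion 4, exclusions 11 and 12).
- Final visit: week 12, ± 3 days.

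**Is the table read correctly?** The study drug dispensing row has the same two marks, baseline and week 4, and the visit text confirms them. Rows that should run to week 12, such as vital signs, do so. The empty week 8 and week 12 cells are therefore unlikely to be a fault of text extraction.

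**Dates**
- Last test: 4 × 7 = day 28 (25 to 31).
- End of dosing: 8 × 7 = day 56 (53 to 59).
- End of avoidance at 4 weeks: 56 + 28 = day 84 (81 to 87).

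**Dosing after the last test**
- Nominal: 56 − 28 = 28 days; 28/56 = 50%.
- Range: 53 − 31 = 22 days to 59 − 25 = 34 days.

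**Avoidance period after the last test**
- Nominal: 84 − 28 = 56 days; 56/84 = 67%.
- Range: 81 − 31 = 50 days to 87 − 25 = 62 days.

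**Post-dose part alone.** All 28 days from day 56 to day 84 come after the last test, so none of the post-dose period is followed by a scheduled test.

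**Detection lag.** A test becomes positive only some time after conception, and the documents give no figure for this. If the lag is L days, conceptions from day 28 − L onward escape the week 4 test, and the uncovered period is 56 + L days. The 56 days above is the value at L = 0 and so a minimum on the nominal calendar.

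**One month or 4 weeks.** With a month of 30 or 31 days the avoidance period ends on day 86 or 87 instead of day 84. The 2 to 3 days' difference lies within the ± 3-day window of the week 12 visit and does not change the finding.

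**The case against.** The strongest reply is that the schedule is coherent as it stands. The urine tests fall at exactly the two visits where drug is dispensed, so the plan tests before each supply is handed over. The eligibility items impose contraception and avoidance of pregnancy; they do not promise testing to week 12. Women must also agree to two highly effective contraceptive methods, which lowers the chance of any pregnancy. All of this stands, and it is why the point is a gap in coverage and not an internal contradiction. It does not close the gap: a test at week 4 cannot show whether the supply dispensed that day was later taken during a pregnancy.

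Several stronger readings are tempting and are not supported:
- *Any pregnancy conceived on drug would go undetected.* The week 4 test is itself on drug and can pick up an earlier conception. A later one could still emerge from the woman's report or from the assessments at weeks 8 and 12, though only if she already knows or suspects.
- *The trial would report no exposed pregnancies because it never looked.* It looks at week 4; it does not schedule a test afterwards.
- *The 67% is a chance of missing a pregnancy.* It is a share of calendar days, not a probability.
- *The silence of the visit descriptions is separate proof.* Those descriptions are not exhaustive. They also leave out the pregnancy tests that Table 1 does schedule, hepatitis B testing, and the lipid panels at weeks 4, 8 and 12. The finding rests on Table 1.

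The study is also small: 12 subjects are anticipated, and the number of women of childbearing potential is not stated. That limits the expected number of events but not the consequence for a woman affected.

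**Conclusion.** The point holds as a gap in scheduled coverage. No scheduled test would detect a pregnancy conceived too late for the week 4 test, which leaves half of the dosing period, two thirds of the period from first dose to the end of required avoidance, and the whole of the post-dose period without a later test.

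This assumes that Table 1 is the complete testing schedule and that visits fall on their nominal days; the visit windows move the figures by up to 6 days either way. Consent pages are not available, so any instruction to participants on reporting a pregnancy cannot be judged. The number of women concerned could be anything from 0 to the anticipated 12.

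It is a cheap improvement to participant safety and safety reporting. No efficacy endpoint or analysis is affected.

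**What to change.** The sponsor should reconcile the urine pregnancy test row of Table 1, and the visit descriptions, with the 8-week dosing period and with the avoidance period in inclusion 4 and exclusions 11 and 12, so that scheduled testing covers the second half of dosing and the post-dose period. The choice of visits is the sponsor's clinical decision. The week 8 visit and the week 12 or early termination visit already include urine collection, so the gap can be covered without a new visit or extra staff. The same amendment can put the length of the avoidance period in one unit across the three eligibility items, as a tidying matter.

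**Cost.** One urine strip per woman of childbearing potential at each added visit, and a one-row change to the schedule with matching text. If both of those visits were used and all 12 anticipated subjects were such women, that would be at most 12 × 2 = 24 strips.

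**Limit.** A test at the final visit could still miss a conception close to it, so the change narrows the gap without closing it entirely.
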